7.2.5 Patient Global Assessment of Change

At Visits 4 and 6, patients will be asked to respond to a PGAC question asking, "Compared with prior to the study start, how do you feel your breathing is?" on a scale of '1=much worse' to '5=much better', with '3=no change'.

7.2.6 Baseline and Transitional Dyspnea Indexes (BDI and TDI)

The BDI and TDI are interviewer administered ratings of dyspnea severity. It is based on three components that evoke dyspnea in activities of daily living. The BDI is scored from 0 to 12 and is only assessed at baseline. The lower the score the worse the dyspnea severity. The TDI measures the change in dyspnea severity from the baseline as measured by the BDI. It is rated by seven grades ranging from -3 (major deterioration) to +3 (major improvement). The BDI will be performed at Visit 2 and the TDI at Visits 4 and 6.

7.3 Safety Assessments

7.3.1 Adverse Events

Recording and reporting adverse events is described in detail in Section 7.6. Standard procedures for emergency care should be followed for any individual adverse event, whenever clinically needed (decision to be taken by the Investigator).

7.3.2 Laboratory Safety Assessments

7.3.2.1 Local Assessments

All female patients will have a serum pregnancy test at screening (Visit 1) and a urine pregnancy test pre-dose at Visit 2 to Visit 6 according to the study center's standard operating procedures (SOPs).

7.3.2.2 Central Laboratory Assessments

In addition to the laboratory assessments detailed below, unscheduled and/or repeat testing may be performed at the discretion of the Investigator. Any additional laboratory results will also be merged into the final database. Laboratory results will be provided to the Investigator for each patient and each visit. The Investigator should assign whether each abnormal result is not clinically significant or clinically significant by manually annotating a print out of the results.

Verona Pharma plc CONFIDENTIAL Page 46 of 67

A vacutainer blood collection system will be used to collect safety laboratory blood samples; full details will be provided in the laboratory manual. Two samples will be collected at each time point, one sample for hematology using a ethylenediaminetetraacetic acid (EDTA) whole blood collection tube and one sample for biochemistry using a serum clot activator tube. A midstream urine sample will also be collected in a sterile container. Additional sample collection and handling information will be described in the laboratory manual.

Samples will be analyzed at the central laboratory for:

Hematology: hemoglobin, hematocrit, total white cell count, leukocyte differential count and platelet count

Biochemistry: creatinine, total bilirubin, alkaline phosphatase, aspartate aminotransferase, alanine transaminase, gamma-glutamyl transferase, lactate dehydrogenase, creatine kinase, thyroid stimulating hormone, triiodothyronine and thyroxine, glucose, potassium, sodium, calcium, NT-proBNP, hepatitis B and C, and FSH (to confirm post-menopausal status when appropriate)

Urinalysis: leukocytes, blood, ketones, bilirubin, urobilinogen, protein and glucose using a dipstick. In the event of an abnormal dipstick urinalysis result, microscopic urinalysis may be conducted. The referral criteria will be specified in the laboratory manual

Any change in laboratory normal ranges during the trial should be forwarded to the Sponsor or designee in a timely manner.

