6.2. Clinical Laboratory Evaluations

- Change from baseline to Week 1 (Visit 3) in laboratory parameters
- Change from baseline to End of Study (Visit 6) in laboratory parameters

Laboratory parameters to be analyzed are:

- Hematology: hemoglobin, hematocrit, total white cell count, leukocyte differential count and platelet count
- Biochemistry: creatinine, total bilirubin, alkaline phosphatase, aspartate aminotransferase, alanine transaminase, gamma-glutamyl transferase, lactate dehydrogenase, creatine kinase, thyroid stimulating hormone, triiodothyronine and

thyroxine, glucose, potassium, sodium and calcium

- Urinalysis: leukocytes, blood, ketones, bilirubin, urobilinogen, protein and glucose.

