6.2.1. Analysis of Clinical Laboratory Evaluation

Descriptive statistics (number of observations, mean, standard deviation, minimum, median and maximum values) for collected values and change from baseline will be summarized for clinical laboratory tests (hematology, biochemistry and urinalysis) at applicable visits, by treatment groups.

Selected laboratory test results will be classified by markedly abnormal criteria as normal or abnormal, according to Table 3 below. The number and percentage of patients with markedly abnormal laboratory results will be provided. No statistical testing will be performed on laboratory data.

Table 3: Markedly abnormal ranges for clinical laboratory parameters

Parameter	Markedly Abnormally High Criteria
Alanine Amino Transferase (ALT)	>3 times Upper Limit of Normal Range
Alkaline Phosphatase	>3 times Upper Limit of Normal Range
Aspartate Amino Transferase (AST)	>3 times Upper Limit of Normal Range
Creatinine	221 $\mu\text{mol/L}$
Gamma Glutamyl Transferase (GGT)	>3 times Upper Limit of Normal Range
Total Bilirubin	>3 times Upper Limit of Normal Range

In addition, abnormal values (relative to the normal range) for hematology and biochemistry will be presented by treatment, patient, visit, and parameter in data listings (including all values of a parameter if at least one value was abnormal per patient). These listings will include: treatment, subject identifier, the laboratory parameter, units, visit number and study day, parameter value, an indicator for values outside of the reference range (H or L), the reference range, and an indicator for clinically significant out-of-range values.

All laboratory parameter results will be listed.

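### SAP 6.2.1 assigns mean, SD and change from baseline to dipstick urinalysis, in conflict with SAP 3.7 and Protocol 9.2.2.6; it should specify category counts and shift tables.

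*Protocol*

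**What the plan says.** **Collection.** Protocol 7.3.2.2 defines the urine tests: "Urinalysis: leukocytes, blood, ketones, bilirubin, urobilinogen, protein and glucose using a dipstick". It adds: "In the event of an abnormal dipstick urinalysis result, microscopic urinalysis may be conducted". By the schedule of assessments, laboratory safety tests are done at screening, Visit 3 (Week 1) and Visit 6 (Week 4).

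**Analysis.** SAP 6.2 defines the laboratory endpoints as change from baseline to Week 1 and to End of Study, and lists the same seven analytes: "Urinalysis: leukocytes, blood, ketones, bilirubin, urobilinogen, protein and glucose". SAP 6.2.1 then gives the statistics: "Descriptive statistics (number of observations, mean, standard deviation, minimum, median and maximum values) for collected values and change from baseline", which "will be summarized for clinical laboratory tests (hematology, biochemistry and urinalysis) at applicable visits, by treatment groups".

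**Abnormal results.** SAP Table 3 sets markedly-abnormal limits for six blood chemistry tests. A further output is restricted to blood: "abnormal values (relative to the normal range) for hematology and biochemistry will be presented by treatment, patient, visit, and parameter in data listings". All laboratory results, urine included, appear in a full listing.

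**General rules.** SAP 3.7 summarises categorical parameters by number and percentage per category, with all five treatment groups in every analysis table. Protocol 9.2.2 has the same rule for categorical variables. For safety data, Protocol 9.2.2.6 applies change from baseline to continuous variables and adds shift tables between low, normal and high.

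**The concern.** A dipstick is ordinarily read in ordered grades. On such a scale the distance between grades has no defined size, so a mean, an SD or a difference from baseline takes its meaning from whatever numbers are attached to the grades. SAP 6.2.1 nevertheless prescribes those statistics for urinalysis by name.

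Laboratory safety tests, including urinalysis, are among the secondary endpoints in Protocol 9.2.1.2, and Protocol 3.2 gives dose-dependent safety as a purpose of the design. The useful question for urine is how many patients in each group moved from a negative to a positive result, or to a higher grade. A mean of coded grades does not answer it. A programmer following SAP 6.2.1 literally would either produce a table of arbitrary numbers or have to choose an alternative after the plan was final.

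**Working it through.** The plan states no figure on this point, so there is none to reproduce. The check is a comparison of sections.

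1. **Is urinalysis within the continuous summary?** Yes. SAP 6.2.1 covers "clinical laboratory tests (hematology, biochemistry and urinalysis) at applicable visits, by treatment groups". Urinalysis is named in the rule.

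2. **What type of data is it?** The analytes in SAP 6.2 are the same seven that Protocol 7.3.2.2 reads by dipstick. The SAP does not repeat the method or give a scale. Graded reporting is therefore an assumption, though the ordinary one.

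3. **Which statistics fail under that assumption?** Minimum, median and maximum can be read off ordered grades. Mean, SD and change from baseline cannot, unless the grades are coded as numbers, and the result then varies with the coding (for example, whether a trace reading counts as a full step or a half step). The SAP gives no coding.

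4. **How does the rule sit with the others?**

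| Source | Rule | Agrees with SAP 6.2.1 for graded urine results? |
|---|---|---|
| SAP 3.7 | Number and percentage per category for categorical data | No |
| Protocol 9.2.2 | Number and percentage for categorical data | No |
| Protocol 9.2.2.6 | Change from baseline for continuous variables | No |
| Protocol 9.2.2.6 | Shift tables for safety data | No laboratory shift table in SAP 6.2 or 6.2.1 |

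5. **Is the difference from the Protocol declared?** No. SAP 3.4 lists two changes: the move from LOCF ANCOVA to MMRM for the primary endpoint, and the added per-protocol set. SAP 6.3.1 does specify a shift table for the ECG interpretation, so the SAP spells out such a table where it wants one.

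6. **Does another output in SAP 6.2.1 fill the gap?** Not by treatment group. Table 3 has no urine parameter, the abnormal-value listing is limited to hematology and biochemistry, and the full listing is by patient.

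7. **Extent.** Seven parameters × two post-baseline visits × five groups = 70 parameter-by-visit-by-group summaries, each with a value and a change. This counts the table positions affected; it does not measure clinical importance.

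**The case against.** The strongest reply is that the documents already contain the right rule. SAP 3.7 requires counts and percentages for categorical parameters without exception and for all five groups. Protocol 9.2.2.6 plans shift tables, and the SAP, which is based on that protocol, never says they are dropped. A sensible programmer would follow those and treat the wording of SAP 6.2.1 as loose.

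Much of this stands. A reader might infer that no valid by-dose summary of urine findings is planned, or that a signal could appear only in the patient listing. The documents do not support either reading, because the general rules would yield a valid summary if urine results were handled as categorical. What remains is that a specific instruction naming urinalysis contradicts them. The low/normal/high layout in Protocol 9.2.2.6 would also need adapting to dipstick grades, which the SAP does not do.

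Three other replies also stand:

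- A reader might take every urine result to be a dipstick category. Protocol 7.3.2.2 allows microscopy after an abnormal dipstick, so the point covers the seven planned parameters only.
- The gaps in the abnormal-value outputs are weak evidence by themselves. Table 3 covers selected tests and omits hematology too, and a listing built on normal ranges with high and low flags can reasonably leave out dipstick results.
- A reader might infer that clinical-significance judgements would be lost because the Investigator records them "by manually annotating a print out of the results". The indicator in SAP 6.2.1 belongs to the hematology and biochemistry listing, Protocol 8.2 names laboratory reports as source data, and Protocol 8.3 provides for transcription from medical records to the eCRF. No gap is shown.

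**Conclusion.** The point holds as a contradiction between SAP 6.2.1 and three other rules: SAP 3.7, Protocol 9.2.2 and Protocol 9.2.2.6. Followed as written, SAP 6.2.1 produces urine summaries that are undefined or depend on arbitrary coding, so this is an unsuitable stated rule and not merely missing detail.

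It rests on one assumption, that dipstick results are reported in grades. If the laboratory transmits measured numerical values for some parameters, the point does not apply to those; depending on the scale, it touches anything from none to all seven.

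The size is minor. Only descriptive safety reporting is affected. SAP 6.2.1 plans no statistical testing of laboratory data, and nothing here bears on the primary analysis, error control or sample size. The documents give no rate of urine abnormalities, so no effect on a safety conclusion can be quantified.

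**What to change.** In SAP 6.2.1, remove urinalysis from the mean, SD and change-from-baseline summary. For each dipstick parameter, give by treatment group:

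- the number and percentage of patients in each category at baseline, Week 1 and Week 4 (Visit 6);
- a shift table from baseline category to the category at Week 1 and at Week 4;
- the number and percentage of patients with a new or worsened positive result.

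State the reporting scale and the order of the grades. Flag abnormal urine results in the listings.

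The cost is one sentence in the SAP and one table shell. The data are already collected, so nothing further is asked of patients or sites.

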7.3.3 Vital Signs

Blood pressure and pulse rate will be measured at screening (Visit 1) and pre-dose, 30 minutes and 1, 2, 4, 6, 8 and 12 hours post-dose at Visit 2 and Visit 6.

Blood pressure and pulse rate will be measured at pre-dose and 30 minutes, 1, 2 and 3 hours after dosing at Visits 3 to 5.

At each time point, a 10 minute window will apply and supine vital signs will be assessed while the patient has been at rest for at least 5 minutes.

7.3.4 Physical Examination

A full physical examination, covering major body systems (assessments of the nose, throat, skin, thyroid gland, neurological system, respiratory system, cardiovascular system, abdomen [liver and spleen], lymph nodes and extremities) will be performed at screening (Visit 1). Results will be recorded in the eCRF as normal, abnormal not clinically significant or abnormal clinically significant. A comment will be made for any clinically significant abnormalities. The physical examination will be repeated at the end of study visit (Visit 6), and any changes only recorded.

7.3.5 12-Lead ECG

12-lead ECGs will be taken at screening (Visit 1) and pre-dose and 2 hours post-dose at all subsequent visits.

Verona Pharma plc CONFIDENTIAL Page 47 of 67

At each time point, 12-lead ECGs should be taken after at least 5 minutes in the supine position. An overall assessment (normal, abnormal not clinically significant or abnormal clinically significant) will be recorded in the eCRF. The ECGs will be centrally collected and analyzed.

7.3.6 Holter Monitors

Holter monitors will be placed at screening (Visit 1) and at end of study (Visit 6). Patients will return to the clinic for removal of the monitors after 24 hours of data has been collected.

7.4 Pharmacokinetic Assessments

Pharmacokinetic analyses will be performed on samples taken from all patients. Blood samples (4 mL at each time point) will be collected prior to dosing at Visits 3 and 6. Samples will be collected by venipuncture in the forearm into lithium heparin tubes and then centrifuged within 15 minutes of collection. The plasma will be separated in a centrifuge at 1100g for 15 minutes and then transferred into polypropylene tubes in two aliquots. After appropriate labelling, the plasma samples will be stored at or below -20°C. The plasma samples will then be transported in dry ice to an external laboratory where they will be stored at or below -20°C until they are submitted for analysis with a validated method. Analyses will be performed by the pharmacokinetic central laboratory.

7.5 Appropriateness of Measurements

The assessments planned in this study are recognized as reliable, accurate and relevant.

Spirometry is a standard lung function test used to screen for, and monitor, respiratory disease. Spirometry and daily calibrations will be performed in accordance with ATS/ERS task force standardization guidelines (Miller et al., 2005) using equipment provided by the spirometry vendor.

Physical examinations, vital signs, 12-lead ECGs, adverse event recording and laboratory safety tests are standard assessments of safety and tolerability. The range of assessments to be performed is deemed appropriate to detect any safety signals.

7.6 Handling of Adverse Events and Pregnancies

7.6.1 Adverse Event Definitions

Adverse event is defined as any undesirable experience occurring to a patient, or worsening of patient's pre-existing condition, during a clinical study, whether or not considered related to the study medication. An adverse event may be any of the following:

- A new illness
- An exacerbation of a sign or symptom of the underlying condition under treatment or of a concomitant illness
- Unrelated to participation in the clinical study or an effect of the study medication
- A combination of one or more of the above factors

No causal relationship with the study medication is implied by the use of the term "adverse event."

An exacerbation of a pre-existing condition or illness is defined as a more frequent occurrence or as an increase in the severity of the pre-existing condition or illness during the

Verona Pharma plc CONFIDENTIAL Page 48 of 67

study. COPD exacerbations, for the purposes of this protocol, are defined as an increase or new onset of more than one respiratory symptom (cough, sputum, sputum purulence, wheezing, or dyspnea) lasting for at least 3 days and requiring treatment with an antibiotic, systemic steroid, or both (Decramer et al., 2009).

Planned or elective surgical or invasive procedures for pre-existing conditions that have not worsened are not adverse events. However, any complication that occurs during a planned or elective surgery is an adverse event (if the event fits the serious criteria, such as an extended hospitalization, it will be considered to be serious). Conditions leading to unplanned surgical procedures may be adverse events.

Adverse reaction is defined as all untoward and unintended responses to study medication related to any dose administered.

Serious adverse event (SAE) is any adverse experience that:

- Results in death
- Is life-threatening
- Requires inpatient hospitalization or prolongation of existing hospitalization
- Results in persistent or significant disability/incapacity, OR
- Is a congenital anomaly/birth defect
- Other medical events*

*Important medical events that may not be immediately life-threatening or result in death or hospitalization may be considered a SAE when, based on appropriate medical judgement, they may jeopardize the patient or may require medical or surgical intervention to prevent one of the outcomes listed above.

An unexpected adverse reaction is an adverse reaction in which the nature or severity of which is not consistent with the Investigator Brochure.

Suspected unexpected serious adverse reactions (SUSAR) is any suspected adverse reaction related to the study medication that is both unexpected and serious.

7.6.2 Recording and Assessing Adverse Events

All adverse events, whether reported spontaneously by the patient, in response to open questioning on treatment days or observed by the Investigator or his/her staff, will be recorded from informed consent until the Telephone Follow-up (2 weeks after Visit 6b).

The start and stop time will be recorded and adverse events will be assessed by the Investigator for the following:

7.6.2.1 *Severity*

Mild: Resolved without treatment

Moderate: Resolved or was tolerated with specific treatment without affecting

study activities

Severe: Did not resolve or was not tolerated with treatment

7.6.2.2 *Chronicity*

Single occasion: Single event with limited duration

Intermittent: Several episodes of an event, each of limited duration Persistent:

Event which remained indefinitely

Verona Pharma plc CONFIDENTIAL Page 49 of 67

7.6.2.3 *Causality*

The Investigator will assess causal relationship between the study medication and each adverse event, and answer "yes" or "no" to the question, "Do you consider that there is a reasonable possibility that the event may have been caused by the study medication?"

For SAEs, causal relationship will also be assessed for study procedures, additional study medication, and other medication. Note that for SAEs that could be associated with any study procedure, the causal relationship is implied as "yes".

A guide to the interpretation of the causality question is found in Appendix II.

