7.6.2.4 Action and Outcome

- Action taken with study medication (none, study medication stopped, study medication temporarily interrupted)
- Other actions (none, concomitant medication, study discontinuation, hospitalization, other)
- The outcome and date of outcome according to the following definitions:
 - Recovered or resolved (adverse event disappeared)
 - Recovering or resolving (patient is recovering)
 - Not recovered or not resolved (adverse event remains without signs of improvement)
 - Recovered or resolved with sequelae (adverse event has resulted in permanent disability or incapacity)
 - Fatal
 - Unknown (only applicable if patient has been lost to follow-up)
- Seriousness (yes or no)

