Average EXACT-PRO total scores, average daily use of rescue medication, SGRQ-C total scores, MRC, global assessment of change, and TDI scores will be compared between the five treatments using ANCOVA models with treatment and country(/center) as factors and using baseline as a covariate where appropriate. Subdomain scores of the EXACT-PRO and SGRQC will be summarized and subjected to exploratory analyses.

The number of COPD exacerbations will be summarized by treatment group.

Testing for efficacy will start with the highest dose of RPL554 versus placebo. If a statistically significant difference is found, the testing will proceed with the next highest dose, and so on. Secondarily, the various doses of RPL554 will be compared. Appropriate measures will be taken to control for the type I error rate in these hypothesis tests. A closed testing procedure to test active dose vs. placebo will be used for the primary endpoint. The study is not powered for pairwise differences between active doses. Thus, dose-response is best investigated in a secondary analysis fitting an appropriate dose-response model to the data. The Statistical Analysis Plan will provide additional details of the multiplicity adjustment method(s) used.

All hypothesis testing will be done using two-sided alternative hypotheses. P-values less than 5% will be considered statistically significant.

9.2.2.6 *Safety*

Safety data, including safety laboratory tests, ECG parameters, Holter monitors, vital signs and physical examinations, will be summarized by treatment group and time point, when appropriate. For continuous variables, the change from baseline (both regarding pre-dose at Visit 2 and pre-dose at each treatment visit) to each post-dose time point will also be calculated and summarized. Data will further be illustrated by shift tables (showing changes from low/normal/high) and shift plots for selected time points.

Coded adverse event terms will be presented by system organ class (SOC) and preferred term and summarized by treatment group. A summary table by treatment group with total number and number of patients with adverse events, SAEs, adverse events leading to discontinuation of study medication, causally related adverse events and severe adverse events will be produced. Further SAEs, causally related adverse events and adverse event of each intensity will be summarized by SOC and preferred term.

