6.1. Adverse Events

Treatment Emergent Adverse Events (TEAEs) are defined as all AEs which start after the first dose of study medication, or start prior to first dose of study medication and worsen, based on the investigator assessment of severity, on or after first dose of study medication.

Adverse events with completely missing onset dates will also be considered as treatment emergent. If any AE records contain only partial dates, these will be handled by imputation, as described in Section 3.8.4.

Table summaries will be produced summarizing AEs in the following ways:

- TEAEs
- TEAEs classified by maximum severity
- TEAEs classified with relationship to study medication
- TEAEs leading to study discontinuation
- Serious TEAEs
- Serious TEAEs classified by maximum severity
- Serious TEAEs classified with relationship to study medication
- Serious TEAEs leading to study discontinuation
- TEAEs with outcome death

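### Adverse event severity is graded mainly by resolution and treatment, so tables by intensity or maximum severity are unreliable if the definition is applied as written

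*Protocol*

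**What the plan says.** Protocol 7.6.2.1 gives three grades:

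- The lowest grade is worded "Mild: Resolved without treatment".
- The middle grade, Moderate, is worded "Resolved or was tolerated with specific treatment without affecting"; what must be unaffected is the patient's part in the study activities.
- The top grade, Severe, is worded "Did not resolve or was not tolerated with treatment".

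The same section and 7.6.2.4 collect three related items separately:

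- Persistence is a chronicity category, "Event which remained indefinitely".
- Treatment is an action, "Other actions (none, concomitant medication, study discontinuation, hospitalization, other").
- Non-resolution is an outcome, "Not recovered or not resolved (adverse event remains without signs of improvement").

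Neither document contains another severity or intensity scale. Protocol 9.2.2.6 plans a summary that counts severe adverse events and then states that "causally related adverse events and adverse event of each intensity will be summarized by SOC and preferred term". SAP 6.1 lists "TEAEs classified by maximum severity" and the same table for serious events. It also counts an event that began before the first dose as treatment-emergent if the investigator's severity assessment worsens on or after that dose.

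**The concern.** Readers of a severity table expect it to show how intense the events were. Here the Mild grade carries no intensity criterion, and the first limb of Severe turns on non-resolution. An intense event that ends without treatment is Mild even if it was poorly tolerated and disrupted study activities.

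Safety is a secondary objective, and Protocol 3.2 says dose-dependent effects on safety will be examined. If short, intense, self-limiting events became more frequent with dose, the severity tables would place them in the lowest grade.

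The treatment-emergent rule has a related difficulty. A grade that depends on resolution cannot be final while the event continues, so it is unclear what worsening of that grade means for an ongoing event.

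**Working it through.** There is no stated figure to reproduce. The check applies the definitions literally to every combination of four yes/no attributes: resolved, treated, tolerated, affected study activities. That gives 2 × 2 × 2 × 2 = 16 logical profiles. They are not event frequencies.

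Rules used:

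- Mild: resolved and not treated.
- Moderate: treated, resolved or tolerated, and study activities not affected.
- Severe, reading A: not resolved, or treated and not tolerated.
- Severe, reading B: treated, and either not resolved or not tolerated. Here the words on treatment govern both verbs, as they must in the Moderate line.

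| Resolved | Treated | Tolerated | Affected activities | Profiles | Reading A | Reading B |
|---|---|---|---|---|---|---|
| yes | no | either | either | 4 | Mild | Mild |
| yes | yes | yes | no | 1 | Moderate | Moderate |
| yes | yes | yes | yes | 1 | none | none |
| yes | yes | no | no | 1 | Moderate and Severe | Moderate and Severe |
| yes | yes | no | yes | 1 | Severe | Severe |
| no | yes | yes | no | 1 | Moderate and Severe | Moderate and Severe |
| no | yes | yes | yes | 1 | Severe | Severe |
| no | yes | no | either | 2 | Severe | Severe |
| no | no | either | either | 4 | Severe | none |

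Reading A:

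- Exactly one grade: 4 Mild + 1 Moderate + 8 Severe = 13.
- Two grades: 2. No grade: 1. Total 16.
- All 8 unresolved profiles meet Severe.

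Reading B:

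- Exactly one grade: 4 Mild + 1 Moderate + 4 Severe = 9.
- Two grades: 2. No grade: 1 + 4 = 5. Total 16.
- Only the 4 treated profiles among the 8 unresolved ones meet Severe.

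Three results hold on both readings. All 4 resolved, untreated profiles are Mild, whatever their tolerability or effect on activities. One treated, tolerated, resolved profile has no grade. Two profiles meet both Moderate and Severe. The readings differ only for the 4 unresolved, untreated profiles, which include the trivial ongoing event.

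Other sections assume that severity and persistence vary separately. Protocol 9.2.2.6 speaks of intensity, although the only grade collected is this one. Protocol 4.3.1 refers to persistent events whatever their severity, but on reading A a persistent event is always Severe. These passages need to be reconciled.

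**The case against.** The case on the other side has several sound parts.

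- **The scale has some intensity content.** Tolerability and effect on study activities are terms of impact, and neither is an action or outcome field in 7.6.2.4. A reader might infer that severity simply duplicates those fields; it does not. Mild and the first limb of Severe still carry no such term.
- **Trivial ongoing events are not necessarily Severe.** Reading B is natural, and it leaves an untreated ongoing event ungraded. That replaces upgrading with a gap.
- **The two-week call is not the cut-off for resolution.** A reader might infer that anything unresolved at the call becomes Severe. Protocol 7.6.3 follows all events until they abate or stabilise; the call ends routine recording under 7.6.2.
- **The effect on treatment-emergent status is narrow.** It reaches only events that began between consent and first dose. Protocol 7.6.1 also counts worsening of a pre-existing condition as an adverse event. If that is recorded as a new event after dosing, it is treatment-emergent by start date without any grade.
- **Dose-related events would not vanish.** SAP 6.1 and 6.1.1 tabulate events by preferred term and dose group regardless of grade. Relationship, discontinuation and seriousness have their own tables. Serial vital signs, ECG, Holter and bronchospasm summaries measure acute effects directly. A reader might infer that an intense event would be hidden from the safety review; the documents support only that it would be hidden in the severity tables.
- **Investigators may not apply the text literally**, and the eCRF completion instructions are not among the documents.

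These points limit the reach of the concern. They do not remove the missing intensity criterion in Mild, the gap, the overlap or the ambiguity in Severe.

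**Conclusion.** The concern holds in limited form. Followed as written, the scale puts intense self-limiting events in Mild, leaves at least one kind of event ungraded, and is ambiguous for untreated ongoing events. The tables by intensity and by maximum severity, and the worsening limb of the treatment-emergent rule, are therefore unreliable as measures of intensity. It would go too far to call them wrong, because that depends on how investigators graded in practice.

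The number of events affected cannot be computed from the documents. Efficacy results and the other safety outputs are unaffected. The conclusion assumes literal use of 7.6.2.1, no overriding eCRF instruction, and that the condition about study activities applies to both limbs of Moderate. If it applied only to the tolerated limb, the gap common to both readings would close; the grading of intense self-limiting events as Mild and the ambiguity in Severe would remain.

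**What to change.** Redefine the three grades in Protocol 7.6.2.1 by intensity, for example by degree of interference with usual activities, so that every event falls in exactly one. Leave persistence to 7.6.2.2 and resolution and treatment to 7.6.2.4. This costs a short wording change in the protocol and the eCRF completion guideline, with no new data item.

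The SAP is dated 6 March 2018, after the planned study period of June 2017 to January 2018, and its version note refers to use after database lock. If data were already collected on this scale, new wording cannot regrade them. In that case, footnote each severity table with the definition used and present it alongside outcome and action taken. That costs a footnote and some additional tabulation of fields already recorded.
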